The efficacy and safety of dupilumab as monotherapy and with concomitant topical corticosteroids (TCS) were evaluated in three pivotal randomized, double-blind, placebo-controlled, multicenter studies (SOLO 1, SOLO 2, and CHRONOS)^{13,14} in 2,119 patients 18 years of age and older with moderate to severe AD. The efficacy and safety of dupilumab monotherapy in adolescent patients was evaluated in a randomized, double-blind, placebo-controlled, multicenter study (AD-1526)¹⁵ in 251 adolescent patients 12 to 17 years of age with moderate-to-severe AD.

This study aims to provide data on the efficacy and safety of upadacitinib initiated at 15 mg QD and dose escalated based on the clinical response, compared with dupilumab as per its label, after 16 weeks of treatment.

Additionally, this study aims to provide data on the efficacy and safety of upadacitinib initiated at 15 mg QD and dose adjusted based on clinical response in subjects with inadequate response to dupilumab.

Clinical Hypothesis

The primary hypothesis is that upadacitinib, initiated at 15 mg QD and dose escalated based on clinical response will demonstrate superior efficacy compared to dupilumab and will be well tolerated in adult and adolescent subjects with moderate to severe AD who have inadequate response to a systemic therapy.

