3 OBJECTIVES AND ENDPOINTS

3.1 Objectives, Hypotheses, and Estimands

Objectives

Primary

The primary study objective, related to Study Period 1, is to assess the efficacy and safety of upadacitinib, initiated at 15 mg once daily (QD) and dose adjusted based on clinical response, compared with dupilumab as per its label.

An additional objective, related to Study Period 2, is to assess the efficacy and safety of upadacitinib, initiated at 15 mg QD and dose adjusted based on clinical response, in subjects with inadequate response to dupilumab.

The primary efficacy objective is based on the achievement of a composite endpoint of at least a 90% reduction in EASI from baseline (EASI 90) and a Worst Pruritus Numerical Rating Scale of 0 or 1 (WP-NRS 0/1) at Week 16 with the treatment of upadacitinib compared with dupilumab per its label in the Intent-to-Treat (ITT) Population, which consists of all randomized subjects (Section 7.2).

Secondary

The secondary efficacy objectives are based on ranked secondary endpoints as defined in Section 3.3 with the treatment of upadacitinib compared with dupilumab in the ITT Population.

Hypotheses and Estimands for the Primary and Ranked Secondary Endpoints

The hypothesis corresponding to the primary efficacy endpoint (Section 3.2) is:

- The proportion of subjects achieving both EASI 90 and WP-NRS 0/1 at Week 16 in those treated with upadacitinib is greater than those treated with dupilumab.

The estimand corresponding to the primary endpoint is defined using the composite variable strategy, as follows:

- Difference in the proportion of subjects achieving both EASI 90 and WP-NRS 0/1 at Week 16 without the use of rescue medication, regardless of treatment discontinuation, between upadacitinib and dupilumab in the adolescent and adult subjects with moderate to severe AD who have inadequate response to systemic therapy.

The hypotheses and estimands corresponding to the ranked secondary endpoints are summarized below.

- Hypotheses: the proportion of subjects achieving each ranked endpoint in those treated with upadacitinib is greater than those treated with dupilumab

- Estimands: Difference in proportion of subjects achieving each of ranked secondary endpoints without the use of rescue medication, regardless of treatment discontinuation, between upadacitinib and dupilumab in the adolescent and adult subjects with moderate to severe AD who have inadequate response to systemic therapy.

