- **Upadacitinib arm (N = 440):** Daily oral doses of upadacitinib 15 mg QD from the Baseline visit until the Week 16 visit. During Period 1, subjects randomized to upadacitinib 15 mg QD will have their dose increased to 30 mg QD if any of the following parameters is met:
 - Starting at Week 4, subject has a < EASI 50 response
 - Starting at Week 4, subject has a < 4-point improvement from Baseline in WP-NRS (weekly average)
 - Starting at Week 8, subject has a < EASI 75 responseAt Week 16, subjects receiving upadacitinib 15 mg QD or 30 mg QD, will be reassigned based on their EASI response:
 - < EASI 75 will be allocated or continue to receive oral doses of upadacitinib 30 mg QD in Period 2
 - ≥ EASI 75 will complete end of study procedures.
- **Dupilumab arm (N = 440):**
 - Adults: Dupilumab 600 mg (2 × 300 mg dupilumab SC injection) administered at the Baseline visit, followed by dupilumab 300 mg SC injection EOW until the Week 16 visit.
 - Adolescents: Adolescents (12 to 17 years of age and weighing at least 40 kg).

Dose of dupilumab for subcutaneous administration in adolescent patients 12 to 17 years of age with AD.

Body weight of subject at Screening Visit and at each visit:

1. 40 to < 60 kg:
 - Initial dose: 400 mg (two 200 mg injections)
 - Subsequent doses (EOW): 200 mg
2. 60 kg or more:
 - Initial dose: 600 mg (two 300 mg injections)
 - Subsequent doses (EOW): 300 mg
- At Week 16, subjects receiving dupilumab as per its label will be reassigned based on their EASI response:
 - < EASI 75 will be offered the option to receive oral doses of upadacitinib 15 mg QD and enter Period 2
 - \geq EASI 75 will complete end of study procedures
- During Period 2, subjects randomized to upadacitinib 15 mg QD will have their dose increased to 30 mg QD if any of the following parameters is met:
 - Starting at Week 20, subject has a < EASI 75 response
 - Starting at Week 20, subject has a < 4-point improvement from Baseline in WP-NRS (weekly average)

An unscheduled visit may be used for this purpose if necessary for dose escalation.

Any subject treated for at least 8 weeks with upadacitinib 30 mg QD with a < EASI 50 response (reduction from Baseline) after rescue with topical corticosteroid treatment for at least 1 week must be discontinued.

[figure not shown]

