7.9 Sample Size Determination

Approximately 880 subjects will be randomized to upadacitinib or dupilumab in a 1:1 ratio. Assuming a response rate of 12% in achieving both EASI 90 and WP-NRS 0/1 at Week 16 in the dupilumab group, this sample size will provide more than 90% power to detect the treatment difference of 17% (upadacitinib versus dupilumab), using a two-sided significant level of 0.05.

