### 10.2.1 Treatment-Emergent Adverse Events

Treatment-emergent adverse events (TEAEs) are defined as follows:

- TEAEs in Period 1 are defined as any adverse events that begin or worsen in severity after initiation of upadacitinib/dupilumab through the minimum (30 days following the last dose of upadacitinib in Period 1 or through 84 days following the last dose of dupilumab in Period 1, the start day of Period 2 – 1).
- TEAEs in Period 2 are defined as any adverse events that begin or worsen in severity after initiation of upadacitinib in Period 2 through 30 days following the last dose of upadacitinib in Period 2.
- TEAEs during the administration of upadacitinib are defined as any adverse events that begin or worsen in severity after initiation of upadacitinib through 30 days following the last dose of upadacitinib.

If a missing or an incomplete onset date is collected for an adverse event, the event will be assumed to be treatment-emergent unless there is other evidence that confirms that the event is not treatment-emergent (e.g., the event end date is prior to the study drug start date). Events where the onset date is the same as the study treatment start date are assumed to be treatment-emergent. All treatment-emergent AEs will be summarized overall, as well as by primary MedDRA SOC and Preferred Term. The SOCs will be presented in alphabetical order, and the PTs will be presented in alphabetical order within each SOC.

The number and percentage of subjects experiencing TEAEs and the number of events per 100 patient-years of exposure will be summarized.

TEAEs per 100 patient-years of exposure are defined as the number of TEAEs divided by the total exposure in 100 patient-years. See the calculation method below:

$$100 * (\text{Number of TEAEs}) / (\text{Total Patient Years})$$

where total patient years is defined as the sum of the study drug duration (defined in Section 6.0) of all subjects normalized by 365.25 and rounded to 1 decimal place.

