## 10.2.2 Adverse Event Overview

The number and percentage of subjects experiencing TEAEs will be summarized for each treatment group for the following AE categories.:

- Any TEAE
- Any treatment-emergent serious adverse events (SAE)
- Any TEAE leading to discontinuation of study drug
- Any severe TEAE (Grade 3 and above according to National Cancer Institute (NCI) Common Terminology Criteria for Adverse Events (CTCAE) version 5.0)
- Any TEAE related to study drug according to the investigator
- Any treatment-emergent SAE related to study drug according to the investigator
- TEAEs of Special Interest
- Other Safety Topics of Interest
- Any TEAE leading to death
- All Deaths
  - Deaths occurring  $\leq$  30 days after last dose of upadacitinib or  $\leq$  84 days after last dose of dupilumab
  - Deaths occurring  $>$  30 days after last dose of upadacitinib or  $>$  84 days after last dose of dupilumab
  - Related to COVID-19

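### Safety against dupilumab is part of the primary objective, but no between-arm estimate or interval is planned for any adverse event, and the counting windows differ by arm

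*SAP*

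**What the plan says.** Protocol 3.1 sets the aim: "The primary study objective, related to Study Period 1, is to assess the efficacy and safety of upadacitinib". The same sentence names dupilumab, used according to its label, as the comparator. The synopsis and SAP 2.1 repeat it, and the trial title also names a comparison of safety. The clinical hypothesis in Protocol 2.1 is that upadacitinib "will demonstrate superior efficacy compared to dupilumab and will be well tolerated in adult and adolescent subjects". It gives no criterion for tolerability.

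The planned adverse event output is by arm. SAP 10.2.1 states: "The number and percentage of subjects experiencing TEAEs and the number of events per 100 patient-years of exposure will be summarized". SAP 10.2.2 states: "The number and percentage of subjects experiencing TEAEs will be summarized for each treatment group for the following AE categories". The rest of SAP 10.2 adds rates per 100 patient-years, tables by system organ class and preferred term, and listings. Protocol 7.5 describes the same kind of output.

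The only confidence intervals in the safety section are for within-arm mean changes in laboratory values (SAP 10.3) and vital signs (SAP 10.4). The primary efficacy endpoint, by contrast, gets a between-arm difference with a 95% CI and p-value (SAP 9.3.2).

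In Period 1, SAP 10.2.1 counts events to 30 days after the last upadacitinib dose or 84 days after the last dupilumab dose, and stops the day before Period 2 starts if that is sooner. SAP 10.2.6 also summarises adverse events of special interest (AESIs) from Baseline to the Week 16 visit.

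**The concern.** The trial asks a comparative safety question and plans no quantity that answers it. Two columns of percentages do not show how large an excess is still compatible with the data. For uncommon events, which include many of the listed AESIs if their rates are low, similar small counts can sit alongside a materially higher risk on one drug.

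A reader could work out a crude difference from the reported counts and denominators. For most overview categories that difference would mix unequal observation times, and the planned tables give no way to correct it. In an open-label trial without an independent monitoring committee, there is also value in fixing the safety contrasts before the data are seen rather than choosing them afterwards.

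**Working it through.** **Inputs from the documents.** "Approximately 880 subjects will be randomized to upadacitinib or dupilumab in a 1:1 ratio" (Protocol 7.9), so n = 440 per arm. Efficacy assumption: 12% vs 29% (12% plus 17 points), two-sided 0.05. Windows: SAP 10.2.1. No adverse event rate is given anywhere, so every event risk below is an assumption.

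**The plan's own figure.** Pooled p = 0.205.
- SE under the null = √(2 × 0.205 × 0.795 / 440) = 0.0272.
- SE under the alternative = √((0.12 × 0.88 + 0.29 × 0.71) / 440) = 0.0266.
- z = (0.17 − 1.96 × 0.0272) / 0.0266 = 4.38, so power is above 99.99%.

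The stated power of more than 90% is reproduced. It concerns efficacy only; no power or precision is stated for safety.

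**What identical counts would exclude.** For x events in each arm, p = x/440 and (l, u) is the Wilson 95% interval for one arm. The Newcombe upper bound for the difference is √((u − p)² + (p − l)²). The risk ratio upper bound is exp(1.96 × √(2/x − 2/440)).

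| Events per arm | p | Wilson l to u | Upper bound, difference | Upper bound, ratio |
|---|---|---|---|---|
| 0 vs 0 | 0% | 0 to 0.87% | +0.9 points | not defined |
| 2 vs 2 | 0.45% | 0.13 to 1.64% | +1.2 points | 7.1 |
| 4 vs 4 | 0.91% | 0.35 to 2.31% | +1.5 points | 4.0 |
| 9 vs 9 | 2.05% | 1.08 to 3.84% | +2.0 points | 2.5 |
| 13 vs 13 | 2.95% | 1.74 to 4.99% | +2.4 points | 2.1 |
| 22 vs 22 | 5.00% | 3.33 to 7.45% | +3.0 points | 1.8 |

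Example, 4 vs 4: √((2.31 − 0.91)² + (0.91 − 0.35)²) = √(1.96 + 0.31) = 1.5 points.

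The statement about doubling is read from the ratio column: the bound is above 2 up to about 3% and below 2 at 5%. The two scales should not be mixed. At 13 vs 13 the difference bound (+2.4 points) is smaller than the observed 2.95%, although the ratio interval still includes 2.

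**The windows.** Take a subject who completes Period 1 and does not enter Period 2. SAP 6.0 takes Week 14 as the last planned dupilumab dose.
- Upadacitinib: about 16 × 7 + 30 = 142 days.
- Dupilumab: about 14 × 7 + 84 = 182 days.
- Gap: about 40 days.

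The exposure-adjusted rates do not remove the gap. Their denominator is study drug duration (SAP 6.0), about 112 days in either arm (dupilumab: 98 + 14). For subjects who enter Period 2 the window closes when that period starts. The net effect across an arm depends on how many enter Period 2, so the documents do not allow it to be sized.

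**The case against.** Descriptive safety reporting is a common and deliberate choice. The documents do not contradict each other on it, and no planned inference depends on it. The plan gives percentages and exposure-adjusted rates as well as counts, and the inputs for a crude difference will be in the tables. All of that stands. It makes this an improvement to the plan rather than an error in it. The crude difference is not a full answer, however, because of the unequal windows.

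Three stronger readings are tempting, and the documents do not support them.

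- *The trial claims comparable safety and lacks a margin.* In Protocol 2.1 the comparison with dupilumab belongs to efficacy. The tolerability wording is absolute, and the formal hypotheses and estimands cover efficacy only. No non-inferiority margin is owed. The point rests on the comparative objective, not on that phrase.
- *Similar counts will be taken as proof of safety.* No section says so. It is only a prediction of how a report might be written, and a tolerability statement could also draw on severity, discontinuations and laboratory findings.
- *The trial is likely to miss a doubling of important events.* This needs an assumed rate and a test that nobody plans. Power for such a test (normal approximation, with Fisher's exact test in brackets) is 23% (15%) for 1% vs 2%, 41% (35%) for 2% vs 4% and 57% (52%) for 3% vs 6%, but 81% (78%) for 5% vs 10%. Nor does a true doubling usually leave no visible excess: the chance that the upadacitinib count is no higher than the dupilumab count is 25% at a 0.5% dupilumab risk, 14% at 1%, 5% at 2% and 0.3% at 5%.

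Intervals for every category would also be numerous and unadjusted, and their limits would reflect sampling error only, not reporting bias in a trial where subjects and site staff know the treatment. Both are good reasons to keep the list short and the label descriptive.

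**Conclusion.** The concern holds as a gap in reporting. The safety half of a comparative primary objective has no between-arm estimate, and unequal windows prevent a reader from recovering a fair one for most overview categories. The efficacy conclusions are unaffected.

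At 440 per arm, identical counts leave an excess of about 0.9 to 2.0 points open for events observed in 0 to 9 subjects per arm. Identical counts would not exclude a doubling at assumed risks of about 3% or less, but would at about 5%. These figures assume full arms of 440 in the safety population, equal observation time and equal observed counts. A reader should not infer that commoner events are poorly covered, or that the plan commits to treating balance in the tables as evidence of equal safety.

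**What to change.** In SAP 10.2.2, 10.2.6 and 10.2.7, for the Safety 1 population:

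- Prespecify the upadacitinib minus dupilumab difference in percentage of subjects with a 95% CI, by Newcombe or Miettinen-Nurminen, which suit sparse counts.
- Use the upadacitinib group regardless of dose. The group that stayed on 15 mg (SAP Table 1) is selected by response after randomization.
- Limit it to a short list: SAEs, severe TEAEs, TEAEs leading to discontinuation of study drug, each main AESI, and key other safety topics.
- Count events over a common window, such as Baseline to the Week 16 visit, which SAP 10.2.6 already uses for AESIs. State how subjects who stop early are counted, since follow-up after the last dose differs by arm.
- Label the intervals descriptive and unadjusted for multiplicity, and state that similar counts alone will not be read as evidence of comparable safety.

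No alpha, formal test or change in sample size is needed. The cost is a common-window derivation for outcomes other than AESIs, added table columns and a few sentences in the SAP. Several intervals will be wide, and their limits will reflect sampling error only in an open-label trial.

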**Dupilumab arm (N = 440):**

Adults: Dupilumab 600 mg (2  $\times$  300 mg dupilumab SC injection) administered at the Baseline visit, followed by dupilumab 300 mg SC injection EOW until the Week 16 visit.

Adolescents: Dose of dupilumab for subcutaneous administration in adolescent patients (12 to 17 years of age and weighing at least 40 kg) with AD will be based on body weight of subject at Screening Visit and at each visit:

- 40 to < 60 kg: initial dose: 400 mg (two 200 mg injections) and subsequent doses (EOW): 200 mg
- 60 kg or more: initial dose: 600 mg (two 300 mg injections) and subsequent doses (EOW): 300 mg

At Week 16, subjects receiving dupilumab as per its label will be reassigned based on their EASI response:

- $<$  EASI 75 will be offered the option to receive oral doses of upadacitinib 15 mg and enter Period 2
- $\geq$  EASI 75 will complete end of study procedures

During Period 2, subjects randomized to upadacitinib 15 mg QD will have their dose increased to 30 mg QD if any of the following parameters is met:

- Starting at Week 20, subject has a  $<$  EASI 75 response
- Starting at Week 20, subject has a  $<$  4-point improvement from Baseline in WP-NRS (weekly average)

An unscheduled visit may be used for this purpose if necessary for dose escalation\*.

Randomization will be stratified by baseline vIGA-AD categories [3;4] and age categories (12 to  $<$  18; 18 to  $<$  40;  $\geq$  40 to  $<$  64 years).

The blinded efficacy assessor will remain blinded to each subject's treatment through Week 32. Subjects and other study site personnel will be aware of the subject's treatment assignment.

\* The subjects are considered as escalating dose to upadacitinib 30 mg QD in analysis if the subjects received the drug dispensation of upadacitinib 30 mg QD.

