### **Study Drug Duration (in Days) in Period 1:**

Duration of upadacitinib in Period 1 is defined for each subject as

- For subjects who do not continue into Period 2:  
Date of the last dose of study drug in the Period 1 - Date of the first dose of study drug in Period 1 + 1

- For subjects who continue into Period 2:  
Minimum of (Date of the first dose of study drug in Period 2 - Date of first dose of study drug in Period 1, Date of the last dose of study drug in Period 1 - Date of first dose of study drug in Period 1 + 1)

Duration of upadacitinib 15mg for subjects who have never experienced dose escalation in Period 1 is defined as

- Date of the last dose of upadacitinib 15 mg in the Period 1 - Date of the first dose of upadacitinib 15 mg in Period 1 + 1

Duration of dupilumab in Period 1 is defined for each subject as

- For subjects who do not continue into Period 2:  
Last dose date of dupilumab in Period 1 - first dose date of dupilumab in Period 1 +14
- For subjects who continue into Period 2:  
Minimum of (Date of the first dose of upadacitinib in Period 2 - Date of first dose of dupilumab in Period 1, Date of last dose dupilumab in Period 1 - Date of first dose of dupilumab in Period 1 + 14)

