### **Study Drug Duration (in Days) in Period 2:**

Duration of upadacitinib in Period 2 is defined for each subject as Date of the last dose of study drug in the Period 2 - Date of the first dose of study drug in Period 2 + 1.

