### **During the administration of upadacitinib (applicable for All UPA Population only):**

Duration of upadacitinib is defined for each subject as the last dose date of upadacitinib - first dose date of upadacitinib +1.

Duration of treatment will be summarized using the number of subjects treated, mean, standard deviation, median, minimum, and maximum. In addition, the number and percentage of subjects in each treatment duration intervals will be summarized:

- ( $\geq 4$  weeks,  $\geq 8$  weeks,  $\geq 16$  weeks) for Period 1
- ( $\geq 4$  weeks,  $\geq 16$  weeks) for Period 2
- ( $\geq 4$  weeks,  $\geq 8$  weeks,  $\geq 16$  weeks,  $\geq 20$  weeks, and  $\geq 32$  weeks) for All UPA Population

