### **During the administration of upadacitinib for All UPA Population:**

- For subjects who took UPA 15 mg QD, then escalate dose to UPA 30 mg QD, the number of planned tablets for UPA 15 mg QD will be used before dose escalation; the number of planned tablets for UPA 30 mg QD will be used after dose escalation, and the number of planned tablets of UPA 30 mg QD depends on the tablet types (15 mg or 30 mg depends on the site).
- For subjects who took UPA 15 mg QD and never experienced dose escalation, the number of planned tablets for UPA 15 mg QD will be used.

Dupilumab compliance is defined as the number of dupilumab injections administered during the subject's participation divided by the number of injections planned during the subject's participation in Period 1. The number of injections planned for dupilumab group in Period 1 is based on protocol Amendment 2.0, i.e., Week 14 dupilumab dose will be the last planned dose for all subjects in the dupilumab group if they complete Period 1.

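### Adverse event rates per 100 patient-years count events up to 30 or 84 days after the last dose but credit almost none of that time, so Period 1 rates can differ between arms with equal on-drug rates

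*SAP*

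**What the plan says.** SAP 10.2.1 defines both halves of the rate.

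- **Events.** The Period 1 window opens at the first dose and runs through "30 days following the last dose of upadacitinib in Period 1 or through 84 days following the last dose of dupilumab in Period 1", or to the day before Period 2 starts if that comes first.
- **Time.** The TEAE count is divided by an exposure total: "where total patient years is defined as the sum of the study drug duration (defined in Section 6.0) of all subjects normalized by 365.25".

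SAP 6.0 defines the duration. For upadacitinib subjects who do not continue, it is last dose minus first dose plus 1 day, so nothing after the last dose day is credited. For dupilumab subjects who do not continue, it is "Last dose date of dupilumab in Period 1 - first dose date of dupilumab in Period 1 +14", which credits 13 days after the last injection day. For those who continue, the duration is capped at Period 2 start; the dupilumab formula begins "Minimum of (Date of the first dose of upadacitinib in Period 2 - Date of first dose of dupilumab in Period 1".

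Period 2 duration runs from the first Period 2 dose to "Date of the last dose of study drug in the Period 2", plus 1 day. For the All UPA population it is "the last dose date of upadacitinib - first dose date of upadacitinib +1". The TEAE window in both cases extends 30 days past the last dose.

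SAP 10.2.4 presents these rates by treatment group for all main event categories, including deaths. Protocol 7.5 fixes the 30- and 84-day windows and asks for rates beside percentages, but defines no denominator. Neither document defines patient-years in any other way.

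On the last dupilumab dose, SAP 6.0 (compliance) says of subjects who complete Period 1 that the "Week 14 dupilumab dose will be the last planned dose for all subjects". SAP 2.3 has adults dosed at Baseline, "followed by dupilumab 300 mg SC injection EOW until the Week 16 visit", which can be read as including a Week 16 dose. These passages must be reconciled; both readings are worked below.

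**The concern.** A rate is interpretable when events and person-time come from the same interval. Here the interval for events is longer, and the excess differs more than twofold between arms. It also applies mainly to subjects who stay out of Period 2. Period 2 entry depends on failing EASI 75 at Week 16, a post-randomisation efficacy outcome that the trial expects to differ by arm. The printed safety rates would then partly reflect efficacy and follow-up rules.

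Safety against dupilumab in Period 1 is part of the primary objective (Protocol 3.1), and the protocol requires these rates. A reader comparing the two columns would take a difference as a difference between drugs.

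**Working it through.** The plan states no rate or exposure total, so there is no figure of its own to reproduce. The check applies its formulas to defined subjects. Day 1 is the first dose.

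**Step 1: one subject who stays out of Period 2.**

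Credited days = last dose day − 1 + 1 (upadacitinib) or last dose day − 1 + 14 (dupilumab). End of event window = last dose day + 30 or + 84. Inflation at a constant rate with full capture = window days / credited days.

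| Subject | Last dose | Credited days | Window days | Uncredited | Factor |
|---|---|---|---|---|---|
| Upadacitinib completer | Day 112 | 112 | 142 | 30 | 142/112 = 1.27 |
| Dupilumab completer, Week 14 last dose | Day 99 | 99 − 1 + 14 = 112 | 183 | 71 | 183/112 = 1.63 |
| Dupilumab completer, Week 16 reading | Day 113 | 113 − 1 + 14 = 126 | 197 | 71 | 197/126 = 1.56 |
| Upadacitinib early stopper (assumed) | Day 42 | 42 | 72 | 30 | 72/42 = 1.71 |
| Dupilumab early stopper (assumed) | Day 29 | 29 − 1 + 14 = 42 | 113 | 71 | 113/42 = 2.69 |

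**Step 2: one subject who enters Period 2 without a gap.** Window and duration both stop at Period 2 start. With a first Period 2 dose on Day 113, both are 112 days, factor about 1.00.

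**Step 3: whole arms.** Assume equal on-drug rates and that all subjects complete. Let fU and fD be the shares staying out of Period 2, and let c be tail capture multiplied by the off-drug rate relative to the on-drug rate. With 30/112 = 0.268 and 71/112 = 0.634, the spurious upadacitinib/dupilumab ratio is

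(1 + 0.268 × c × fU) / (1 + 0.634 × c × fD).

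The documents give none of fU, fD or c; all values below are assumptions.

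| fD | fU | c = 1 | c = 0.5 | c = 0.25 |
|---|---|---|---|---|
| 1.0 | 1.0 | 0.78 | | |
| 0.6 | 0.75 | 0.87 | 0.93 | 0.96 |
| 0.4 | 0.8 | 0.97 | 0.98 | |
| 0.3 | 0.8 | 1.02 | | |
| 0.3 | 1.0 | 1.07 | | |

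With the Week 16 dose reading, the first row is 1.268/1.563 = 0.81. The distortion cancels when fD/fU = 30/71 = 0.42. At c = 1 the formula's extremes are 1/1.634 = 0.61 (fD = 1, fU = 0) and 1.27 (fD = 0, fU = 1).

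**Step 4: add early stoppers.** Suppose 10% of each arm stop early as in Step 1 and nobody enters Period 2. Upadacitinib: (0.9 × 142 + 0.1 × 72) / (0.9 × 112 + 0.1 × 42) = 135/105. Dupilumab: (0.9 × 183 + 0.1 × 113) / 105 = 176/105. Ratio 135/176 = 0.77.

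**Step 5: other rates.** Period 2 completers in either group: 142/112 = 1.27. All UPA: 1.27 at 16 weeks, (224 + 30)/224 = 1.13 at 32 weeks. These have no dupilumab comparator.

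**The case against.** **The formula is open and the rates are descriptive.** The SAP labels the figure as exposure-based and states how it is computed. No safety hypothesis is tested. Percentages do not use this denominator, and special-interest events have a Baseline-to-Week-16 summary (SAP 10.2.6). This limits the consequence. It does not repair the rates: the label names the denominator without making events outside it belong to it, and the Week 16 summary covers special-interest events only.

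**The tail may yield few events.** Follow-up after the last treatment visit rests largely on one visit or call. It is waived for subjects who start commercial drug (Protocol 5.6), and later events in early stoppers who do so become postmarketing reports (Protocol 6.1). This stands: with quarter capture, 0.87 moves to 0.96.

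**The windows come from the protocol.** They do. A reader might infer that the 30/84-day definition is itself the error. The documents do not support that; Protocol 7.5 ties the windows to drug half-life. The fault lies in pairing them with a shorter denominator.

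**Time at risk could be the denominator instead.** That is exact only with full capture and an unchanged rate off drug. At fD = 0.6 and fU = 0.75 it gives 1.06 at half capture and 1.10 at quarter capture, against 0.93 and 0.96 under the SAP formula. It suits a supplement better than the main rate.

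**Conclusion.** The mismatch is real and follows directly from SAP 6.0 and 10.2.1. For completers who stay out of Period 2, it inflates the rate by 1.27 (upadacitinib) or 1.63 (dupilumab, Week 14 last dose), given a constant rate and full capture.

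Three stronger readings are tempting and are not supported. First, that the Period 1 rates as a whole cannot be compared: subjects who enter Period 2 without a gap have no mismatch, and some scenarios come close to cancelling. Second, that the formula necessarily favours upadacitinib: direction depends on Period 2 entry, early stopping and tail capture, none of which the documents give. Third, that 0.78 is the worst case: it describes everyone completing and nobody entering Period 2, and Steps 3 and 4 give values outside it.

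The supported conclusion is that equal on-drug rates can print as different rates, by an unknown net amount. It should be fixed before the safety tables are produced. Efficacy and its error control are unaffected.

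**What to change.** - **Rates (SAP 10.2.1, 10.2.4).** Count only events with onset or worsening inside the person-time in the denominator: either the days credited by Section 6.0 or, for the Period 1 comparison between arms, a common Baseline-to-Week-16 window with matching person-time. Match Period 2 and All UPA rates in the same way.
- **Later events.** Tabulate TEAEs after the credited time separately, as counts by arm.
- **Deaths.** Give deaths after the credited days as counts, not rates, both within and beyond 30/84 days of the last dose.
- **Percentages and listings.** Keep the 30/84-day definition.
- **Record.** State in SAP 14.1 that the rate numerator is narrower than the Protocol 7.5 TEAE definition, or keep the protocol-window rate as a supplement with a footnote on the mismatch.

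The work is SAP wording, one on-treatment flag and one table of later events. SAP 7.2 already uses arm-specific windows of 1 and 14 days after the last dose for concomitant medication, so the flag has a precedent.

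The costs should be stated. Rates and percentages will count different events. Post-treatment events leave the rate. Under the Section 6.0 option, credited time after the last dose still differs for early stoppers (0 v 13 days), so an event the day after the last upadacitinib dose drops out while one 13 days after the last dupilumab dose stays; the common window is cleaner here. The new rates are not directly comparable with tables built on the old formula. The percentages keep their 30/84-day asymmetry, which this change does not address.
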